Live Long Walk Strong SAP

NCT 04026503

8.8.2019

Initially, we will view plots and calculate simple descriptive statistics for all continuous measures, and frequencies and percentages for all categorical variables to examine the data distributions and check for data accuracy and completeness.

Derived variables (change from the baseline to each follow-up visit as well as change between consecutive visits and time intervals between visits) will be calculated and examined.

Two sample t-test will compare mean scores in changes of gait speed (Δ GS) and LLWS target attributes (ATTR) between treatment and control groups at baseline and a t-test for paired samples will evaluate changes between follow-up visits.

Multiple regression models will assess relationships between dependent and independent variables and causal mediation models will be used for mediation analysis. Mixed effects regression models will be used to analyze repeated measures. In regression and mediation models, we will examine and adjust for potential confounding factors (by design or as covariates), including baseline scores (as appropriate), age, sex, BMI, comorbidity-score, etc.

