Title of Study: The Live Long Walk Strong Rehabilitation Program: What Features Improve Mobility Skills?

NCT 04026503

8.8.2019

Primary Outcome: The primary outcome for all aims of this study is usual Gait Speed.^{53,54} Gait speed is recorded by stopwatch over a 4-meter walking course beginning from a standing start. The fastest of 2 trials is recorded in meters/seconds. Declining gait speed is associated with heightened risk for adverse health outcomes (hospitalization, disability, death) over 1-4 years of subsequent follow up.^{53,54} Changes in gait speed of .05 and 1.0m/s are characterized as small and large clinically meaningful differences respectively.^{24,55} For Aims 2 & 3, we will identify factors that mediate changes in gait speed. Our experience with LLWS and related clinical trials identifies that the majority of participants (> 70%) exceed a .09 m/s change after treatment.]

Timing and coordination of gait

Smoothness of walking is our primary measure of timing and coordination and is an integrated measure of motor control of walking.^{37,56} It is assessed during usual over ground walking. Linear acceleration of the body is measured along three axes (vertical, anterior-posterior and medial-lateral) using a tri-axial accelerometer attached to the skin over the lumbar spine (L3 segment). Trunk accelerations are sampled at 200 Hz and used to calculate the harmonic ratio following the methodology of Menz.^{37,56} The harmonic ratio is derived in the vertical, medial-lateral and anterior-posterior directions. Higher harmonic ratios indicate greater levels of functioning. Our prior work reports mean changes of 25-30% in smoothness of walking occur with training.¹⁸

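### The only sentence that compares treatment with control tests change in gait speed at baseline, where the SAP's own definition leaves no change to test

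*SAP*

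**What the plan says.** The Protocol, under Primary Outcome, states: "The primary outcome for all aims of this study is usual Gait Speed". It adds: "For Aims 2 & 3, we will identify factors that mediate changes in gait speed". The outcome is therefore settled, and change in it is what the aims turn on.

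The SAP's paragraph on derived variables defines change as "change from the baseline to each follow-up visit as well as change between consecutive visits". The next paragraph begins "Two sample t-test will compare mean scores in changes of gait speed", adds the target attributes, and places the comparison "between treatment and control groups at baseline and a t-test for paired samples will evaluate changes between follow-up visits".

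The models paragraph then says: "Multiple regression models will assess relationships between dependent and independent variables and causal mediation models will be used for mediation analysis". It continues: "Mixed effects regression models will be used to analyze repeated measures". Adjustment covers potential confounders, "including baseline scores (as appropriate), age, sex, BMI, comorbidity-score, etc".

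**The concern.** The variable in the two-sample test is a change score, and the time point attached to it is the one visit at which that score does not exist. This would be a minor slip if another sentence gave the treatment contrast, but none in the public text does. The t-test sentence is the only one that names the treatment and control groups.

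The slip can be repaired in more than one way, and the repairs give different analyses. An analyst would have to choose between them, and also choose the visit and whether to adjust for baseline. For the outcome that the Protocol makes primary for every aim, those choices belong in the plan before data are seen.

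**Working it through.** The documents state no figure that depends on this sentence, so there is nothing to reproduce. The check has three steps.

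**1. The sentence against the SAP's definition.** Write GS(t) for gait speed at visit t, with t = 0 at baseline. Change from baseline is D(t) = GS(t) − GS(0). At baseline, D(0) = GS(0) − GS(0) = 0 for everyone in both groups. The difference in means is 0 and the pooled SD is 0, so the t statistic is 0/0. The other type of change, between consecutive visits, has no value at baseline either, because no visit precedes it.

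**2. What the sentence could have meant.**

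- *From* baseline was intended. The two-sample test is then a between-group contrast of change. The follow-up visit is still not named.
- A baseline comparison of raw scores was merged with a sentence about change. The two-sample test then compares the groups before any follow-up and says nothing about a treatment effect. What is left is the paired test, which is within-person and is stated without a group comparison.

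The definition one paragraph earlier makes the first reading likelier, but the text does not settle it.

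No other text fills the gap:

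- The regression sentence speaks only of dependent and independent variables.
- The mixed-model sentence gives no treatment term, no treatment-by-visit term and no visit.
- The Protocol's remark about change after treatment (more than 70% of participants exceeding .09 m/s) reports earlier experience.
- The 4-weekly assessments in the Protocol's covariates section are of physical activity and exercise engagement, not gait speed.

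**3. What the choice of estimator is worth.** Assumptions, none given in the documents: random allocation, the same SD s at baseline and follow-up, and baseline-to-follow-up correlation r.

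- Variance per participant of a change score: 2(1 − r)s².
- Residual variance after adjustment for baseline: (1 − r²)s² = (1 − r)(1 + r)s².
- Ratio of change-score to adjusted variance: 2/(1 + r).
- Extra participants needed by the change-score test for equal precision: 2/(1 + r) − 1.

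| r (assumed) | 2/(1 + r) | Extra participants |
|---|---|---|
| 0.5 | 1.333 | 33% |
| 0.6 | 1.250 | 25% |
| 0.7 | 1.176 | 18% |
| 0.8 | 1.111 | 11% |
| 0.9 | 1.053 | 5% |

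Confidence interval width scales with the square root of the ratio. At r = 0.6 the unadjusted interval is √1.25 − 1 = 12% wider; at r = 0.8 it is √1.111 − 1 = 5% wider.

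**The case against.** The best defence is that nobody would run the test literally. Read with the definition just before it, the sentence very probably means change from baseline, and then the defect is a word or two. That stands as an account of intent. It does not correct the text, and the corrected wording would still not say which visit the contrast refers to.

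Three stronger readings are tempting, and the documents do not support them.

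- *The primary analysis of the trial is undefined.* Neither document calls the t-test the primary analysis. It follows the descriptive steps and precedes the regression, mixed and mediation models, any of which may be meant to carry the treatment effect. What can be said is that they do not state it.
- *No primary visit or treatment contrast exists.* The public Protocol is an excerpt on outcomes and covariates. It refers to a section 3.G.vi that is not part of it. A visit schedule and a contrast may be set elsewhere, so the fair request is to state or cross-reference them.
- *A t-test on change is invalid, or the plan ignores baseline.* Under random allocation both the change-score and the baseline-adjusted estimates are valid, and the SAP already plans baseline adjustment in its models where appropriate. That qualifier can be legitimate: a mixed model that keeps baseline as an outcome row would not also carry it as a covariate. The argument for adjustment is precision.

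It is also fair that the percentages rest on an assumed r, and that the open-ended covariate list is a matter of missing detail rather than error.

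**Conclusion.** Wrong as written; should-fix. The sentence contradicts the SAP's own definition of change, and this needs no assumption beyond the text. It is probably a slip, but it falls in the only public sentence that compares the groups, so it should not be left to the reader to repair.

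The gain from replacing an unadjusted change-score test with a baseline-adjusted analysis is conditional. Across r = 0.5 to 0.9 the unadjusted test needs 33% down to 5% more participants for the same precision, given random allocation and equal SDs. If allocation were not random, the two estimators could answer different questions and this comparison would not apply. The contradiction would remain either way.

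**What to change.** Replace the t-test sentence with wording along these lines:

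> The treatment effect is the between-group difference in change in gait speed from baseline to [visit taken from the sponsor's own schedule, stated here or cross-referenced]. It is estimated with the planned regression model or, if there are several follow-up visits, the planned mixed effects model with treatment, visit and treatment-by-visit terms, adjusted for baseline gait speed. The difference at the named visit is reported with a 95% CI. Target attributes are compared in the same way. Baseline scores are summarised by group descriptively. Within-group paired tests are not used to infer a treatment effect.

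If the mixed model keeps baseline as an outcome row, constrain the arms to a common baseline mean instead of adding the baseline covariate.

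The ranking of the target-attribute measures and the exact covariate list are left to the sponsor; this correction does not depend on them.

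The cost is one paragraph of SAP text. It uses models and a baseline adjustment the SAP already mentions, and needs no new data and no change to trial conduct.

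### Change between follow-up visits is assigned to a paired t-test with no control comparison, and the mixed-model sentence that could supply one names no arm-by-visit contrast

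*SAP*

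**What the plan says.** The SAP's second paragraph derives several change variables: "change from the baseline to each follow-up visit as well as change between consecutive visits and time intervals between visits". Its third paragraph then names the tests. A two-sample t-test compares changes in gait speed and in the target attributes "between treatment and control groups at baseline". For later change, "a t-test for paired samples will evaluate changes between follow-up visits". The SAP does not say whether the paired test is run in the treated arm, in each arm, or in both arms pooled.

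The fourth paragraph adds: "Mixed effects regression models will be used to analyze repeated measures". It gives no outcome, no arm-by-visit term and no contrast for that model. Adjustment in the regression and mediation models is for confounders, "including baseline scores (as appropriate), age, sex, BMI, comorbidity-score, etc".

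In the protocol, under Primary Outcome, "The primary outcome for all aims of this study is usual Gait Speed", and the scale of meaningful change is given as follows: "Changes in gait speed of .05 and 1.0m/s are characterized as small and large clinically meaningful differences respectively". Only the .05 m/s figure is used below.

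**The concern.** What happens between follow-up visits bears on whether gains hold, fade or grow. The only test that the SAP expressly ties to that interval compares participants with themselves. Run within the treated arm, it measures programme carry-over plus anything else that moves scores over time: ageing, illness, season, and practice on repeated performance tests. Run on both arms pooled, it cannot isolate the programme at all.

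The error can go in either direction. Natural decline can look like lost benefit, and practice can look like further gain. If controls decline while treated participants hold steady, the paired test in the treated arm shows nothing and a retained benefit is missed. Covariate adjustment does not help, because age, sex, BMI and comorbidity do not remove a shift common to both arms.

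**Working it through.** **What each test estimates.** Let δ be the mean between-visit drift shared by both arms, and τ the programme-related change over the same interval.

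- Paired test, treated arm: δ + τ
- Paired test, equal arms pooled: δ + τ/2
- Treated minus control: (δ + τ) − δ = τ

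Only the third isolates τ. The bias of the treated-arm paired test is exactly δ.

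**Inputs.** The documents state no sample size, SD, alpha or drift, so there is no figure of the plan's own to reproduce. Assumed here: two-sided alpha 0.05; SD of between-visit change 0.10, 0.15 or 0.20 m/s; 30, 60 or 100 per arm; drift 0.02 m/s or 0.05 m/s. The larger drift equals the protocol's small meaningful change; the smaller is 0.02/0.05 = 40% of it.

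**Case 1: shared drift, τ = 0.** The rejection rate of the one-arm paired test comes from the non-central t distribution with n − 1 degrees of freedom and noncentrality (δ/SD)·√n. For example, with δ = 0.02, SD = 0.10 and n = 100, the noncentrality is 0.2 × 10 = 2.0 and the rejection rate is 50.8%.

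| SD (m/s) | n per arm | Paired, δ = 0.02 | Paired, δ = 0.05 |
|---|---|---|---|
| 0.10 | 30 | 18.5% | 75.4% |
| 0.10 | 60 | 33.2% | 96.8% |
| 0.10 | 100 | 50.8% | 99.9% |
| 0.15 | 30 | 10.9% | 42.3% |
| 0.15 | 60 | 17.4% | 71.9% |
| 0.15 | 100 | 26.2% | 91.0% |
| 0.20 | 30 | 8.3% | 26.3% |
| 0.20 | 60 | 11.9% | 47.8% |
| 0.20 | 100 | 16.8% | 69.7% |

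A two-sample test on the same between-visit changes, simulated 10,000 times per setting with both arms falling 0.05 m/s, rejected in 4.5% to 5.3% of trials. The shared drift cancels, so its size does not matter.

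**Sensitivity to smaller drift.** At SD 0.12 with 50 or 100 per arm, the paired test rejects 9% or 13% of the time for a drift of 0.01 m/s, 21% or 38% for 0.02, and 41% or 70% for 0.03. The excess is small if drift is small.

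**Case 2: treated arm steady, control arm falls 0.05 m/s.** The treated-arm paired test rejects in about 5% of trials (simulated 4.6% to 5.4%), whatever the SD and n. The between-arm test has 16% to 94% power over the same grid.

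**Price of the controlled comparison.** The one-arm standard error is SD/√n; the between-arm one is SD·√(2/n). The ratio is √2 ≈ 1.4.

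**The case against.** A reader might infer that the plan as a whole cannot tell drift from programme benefit, or that the trial will claim maintenance on the strength of the paired test. The documents support neither.

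- The SAP assigns repeated measures to mixed effects models, the natural home for between-visit change by arm. The limitation belongs to the paired test; what the plan lacks is a named contrast.
- No section states a durability aim or says what will be concluded from the paired test. The protocol describes Aims 2 and 3 as finding mediators of gait-speed change. The clause precedes the modelling paragraph and may be meant as a preliminary, unadjusted look, although the SAP does not label it so. As within-arm description, a paired test is legitimate.
- The two-sample clause refers to changes, and none exists yet at baseline, so change from baseline may be meant. Arms would then be compared on change to each follow-up visit, which is a controlled answer to whether benefit is still present at that visit. This would narrow the gap but not close it: the increment between visits would still have no between-arm test or interval.
- The documents give no visit schedule or length of control follow-up. The four-weekly assessment of all participants in the protocol's Covariates section covers physical activity and exercise engagement, not gait speed. A concurrent control over the follow-up interval is therefore an assumption.
- Every input to the rejection rates is assumed.

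These points limit the scope and size of the concern. They do not change the fact that the one test expressly linked to follow-up change has no control term.

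**Conclusion.** The point holds for the paired test as specified: used alone, it confounds programme carry-over with shared drift, and nothing in the mixed-model sentence commits the analysis to the contrast that would separate them. It does not show that the SAP excludes a controlled analysis of follow-up change, nor that any conclusion will rest on the paired test.

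The practical size is uncertain. The 8% to 51% range depends on an assumed 0.02 m/s drift and on assumed SDs, arm sizes and alpha; it shows direction and plausible scale, not an expected error rate for this trial. Given how little the change costs, it should be made before the data are analysed, but it concerns interpretation of the follow-up interval and does not invalidate the plan.

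**What to change.** Replace the paired-test clause with:

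> Change between follow-up visits will be compared between treatment and control as the arm-by-visit contrast (difference in change between consecutive follow-up visits) from the planned mixed effects model, with 95% confidence interval. Within-arm paired changes are descriptive only and will not be used to claim maintenance, loss or further gain.

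The sponsor should also confirm that controls are assessed at the same follow-up visits. If they are not, the contrast is unavailable and the SAP should label follow-up change as descriptive only. The two-sample clause in the same sentence should be clarified at the same time, so that it states which change is compared between arms.

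If controls do attend those visits, the cost is a sentence or two of SAP text and one contrast from a model already planned, with no new data. The statistical price is the wider standard error, about 1.4 times that of a one-arm paired difference with equal arms.

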Trunk Extensor Muscle Endurance is measured using a technique that is reliable and valid among community dwelling older adults.³¹ This is measured while the participant is lying prone on a specialized plinth positioned 45 degrees from vertical. Subject's feet are supported on a footplate and fixed in position. A portion of the table that is hinged and positioned at waist level is lowered to the horizontal plane and subject is asked to maintain their position as long as possible with their arms across his chest. The test is terminated when the subject can no longer maintain the unsupported position or after 150 seconds. Time is recorded in seconds and only one trial is performed. Reliability for the trunk measure is excellent ($r = .88-91$).³¹ We have observed mean changes of 48% with LLWS (see study 3, preliminary work).

Self-Efficacy Scale for Exercise is an established, reliable and valid scale measuring an individual's confidence to engage in exercise.^{45,62} It is sensitive to change and successfully utilized within studies of older adults with mobility problems, including our previous RCT among hip fracture patients.^{45,62}

Secondary Outcome Measures: [The SPPB total score will be a secondary outcome for each aim. The SPPB is a well-established, valid and reliable physical performance measure used extensively in aging research. It is a composite measure of three functional tasks: usual gait speed over 4 meters from a standing start, 5 times repeated chair stand, and progressive standing balance. Each task is scored between 0-4 (higher score corresponds to better performance), with a maximum summary score of 12. Each increment decline in SPPB total score is associated with heightened risk for adverse health outcomes.^{53,54} Changes in SPPB of 0.5 units and 1.0 units are characterized as a small and large clinically meaningful differences respectively.^{24,55} The Late Life Function and Disability Instrument (LLFDI) will also be a secondary mobility outcome. The LLFDI is a reliable patient-reported (by interview or phone) measure of functional mobility validated in a wide range of older adult populations, having been used in over 70 clinical trials worldwide.⁶³ We have previously reported that LLFDI-Function and its sub domains are very sensitive to change.³⁵ Scores for all domains are scaled between 0-100 and clinically important differences are defined.]⁶⁴

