Covariates & potential confounding variables: Clinical characteristics including age, gender, educational attainment, race, and marital status will be recorded. Height and weight will be measured using standardized methods and body mass index (BMI) will be calculated as weight (kg) divided by height in squared meters.⁶⁵ Comorbidity will be measured using a valid and reliable questionnaire that allows for the characterization of whether these conditions require treatment or impact physical function.⁶⁶ Depression will be measured by the 10-item Center for Epidemiologic Studies-Depression Scale (CES-D),^{67,68} a widely used screening tool for symptoms of depression that discriminates well between general population samples. The Brief Pain Inventory questionnaire will measure pain.^{69,70} Falls, fall related injuries and illnesses will be recorded via monthly calendars.⁷¹ Also, we will administer the Activities-specific Balance Confidence (ABC) Scale, which is a well-established and validated scale measuring confidence with balance and mobility.^{62,72} Given the strong association between mobility skills and cognition, participants will also undergo the NIH toolbox cognition battery.⁷³ Knee and ankle range of motion will be measured using a goniometer. Maximal knee flexion and extension are measured in degrees, while the ankle range of motion is measured as a binary measure for both dorsiflexion (ability or inability to dorsiflex to 90 degrees) and plantarflexion (ability or inability to plantarflex 20 degrees). Reliability for this measure is excellent (r=.82-.98).⁷⁴ [Every 4 weeks of study participation, we will assess physical activity and exercise engagement among all participants. Physical activity will be measured via the Phone-Fitt,⁹ a measure ascertainable by phone or in person that is validated against actigraphy measures. Exercise engagement will be measured by self-report as specified in section 3.G.vi.]

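### The only stated treatment-control comparison is a t-test on change that omits anyone without both visits; the mixed model already named should carry it, with a stated missing-data method

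*SAP*

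**What the plan says.** The SAP's second paragraph defines the derived variables as "change from the baseline to each follow-up visit as well as change between consecutive visits". The third paragraph gives the comparison of treatment and control: "Two sample t-test will compare mean scores in changes of gait speed" and in the target attributes. That clause ends by placing the comparison at baseline, where no change yet exists, so its time point is unclear. The same sentence adds the within-participant test: "a t-test for paired samples will evaluate changes between follow-up visits".

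The fourth paragraph names multiple regression for relationships between variables and continues: "causal mediation models will be used for mediation analysis. Mixed effects regression models will be used to analyze repeated measures". It does not say which of these models estimates the arm difference. No analysis set, missing-data assumption, imputation or sensitivity analysis appears. The nearest text is a descriptive check of completeness in the first paragraph.

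In the protocol the primary outcome is a performance test: "Gait speed is recorded by stopwatch over a 4-meter walking course beginning from a standing start". Smoothness of walking, leg power and trunk endurance are also physical tests, and no remote version is described. Other data are collected between visits or can be obtained remotely:

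- "Falls, fall related injuries and illnesses will be recorded via monthly calendars".
- "Every 4 weeks of study participation, we will assess physical activity and exercise engagement among all participants".
- "The LLFDI is a reliable patient-reported (by interview or phone) measure of functional mobility".

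The SAP gives none of these a role when a visit is missed.

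**The concern.** A change score exists only when both visits are observed. A t-test on change therefore drops a participant who misses the later visit and ignores any interim gait speed that person supplied. The paired tests run on a different subset at each interval, so successive within-participant changes need not describe the same people.

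Stopping attendance in a rehabilitation trial may well be related to how the participant is doing. If it depends on gait speed already seen, and does so differently by arm, the difference among attenders is not the difference between the groups as assigned. The protocol's Primary Outcome section treats 0.05 m/s as a small meaningful change, so a bias of 0.01 m/s is one fifth of the effect of interest.

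For Aims 2 and 3, a missed visit removes gait speed and the performance-based mediators together, so a default fit of the mediation models describes attenders.

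**Working it through.** **Inputs.** From the protocol: 0.05 m/s as the small meaningful change, used here as the true arm difference. The documents give no sample size, SD of change, dropout rate or visit correlation, so there is no plan figure to reproduce. Assumed: SD of change 0.15 m/s at both visits; correlation 0.6 between interim and final change; interim effect 0.6 times the final effect; every participant has the interim visit; dropout before the final visit is 10-20%.

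**Formula.** In one arm, completers' mean minus the mean of everyone = d × g, where d is the share missing and g is the gap between completers' and dropouts' mean change. The bias of the arm difference is d_T × g_T − d_C × g_C. It is zero when both products are equal, including when both gaps are zero. Its sign depends on which product is larger.

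**By hand.** If one arm has a gap of 0.05-0.09 m/s and the other has none:

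- 10% missing: 0.10 × 0.05 = 0.005 to 0.10 × 0.09 = 0.009 m/s.
- 20% missing: 0.20 × 0.05 = 0.010 to 0.20 × 0.09 = 0.018 m/s.

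**Simulation.** Dropout is logistic in the standardised interim change, with slope 1 or 1.5 (odds ×2.7 or ×4.5 per SD worse). The intercept is solved to give the stated dropout. The true difference is 0.050 m/s.

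| Dropout pattern | t-test on observed change | Using the interim visit |
|---|---|---|
| Treated only selective, 10% per arm, slope 1 / 1.5 | 0.058 / 0.060-0.061 | 0.050 |
| Treated only selective, 15% per arm, slope 1 / 1.5 | 0.062 / 0.065-0.066 | 0.050 |
| Treated only selective, 20% per arm, slope 1 / 1.5 | 0.066 / 0.070-0.071 | 0.050 |
| Treated only selective, slope 0.25 to 0.5 | 0.052 to 0.059 | 0.050 |
| Control only selective, 15% per arm, slope 1 | 0.038 | 0.050 |
| Both selective (slope 1), 20% treated, 10% control | 0.058 | 0.050 |
| Random, or equally selective at equal rates | 0.050 | 0.050 |

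The last column is 0.050 to within simulation error (0.049-0.051 across runs). Ranges in the middle column are differences between simulation runs.

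In relative terms: 0.058/0.050 = 1.16 and 0.070/0.050 = 1.40, overstatements of 16% to 40%; 0.038/0.050 = 0.76, an understatement of 24%. The selective scenarios are strong. At 20% dropout and slope 1, the implied gap is (0.066 − 0.050)/0.20 = 0.08 m/s; at slope 1.5 it is (0.070 − 0.050)/0.20 = 0.10 m/s.

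**What the phone and calendar data add.** With an auxiliary of correlation ρ with gait-speed change, variance relative to full data is (1 − ρ²)/(1 − d) + ρ². At d = 0.20:

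- ρ = 0: 1/0.80 = 1.25
- ρ = 0.3: 0.91/0.80 + 0.09 = 1.23
- ρ = 0.5: 0.75/0.80 + 0.25 = 1.19
- ρ = 0.7: 0.51/0.80 + 0.49 = 1.13

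For bias, replacing the interim visit by such an auxiliary (20% dropout, treated only selective) moves 0.066 to 0.064 and 0.070 to 0.067 at ρ = 0.3, and to 0.059 and 0.063 at ρ = 0.5. If dropout depends on the unobserved gait-speed change itself (about 21% missing), a completer bias of about 0.18 SD falls only to 0.17, 0.14 or 0.10 SD at ρ = 0.3, 0.5 or 0.7. It goes to about zero only if the auxiliary itself explains the missingness.

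**The case against.** The strongest reply is that the t-tests may be preliminary. They follow the descriptive steps, and the adjusted regression, mixed and mediation models may be the intended main analysis. A likelihood-based mixed model keeps participants with partial follow-up. That reading is fair, but the SAP does not state it: the only sentence that names the two groups is the t-test sentence. If it is the intent, the first part of the fix merely writes it down.

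Four stronger readings are tempting, and the documents support none of them.

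- A reader might infer that the t-test will overstate the benefit. The direction depends on which arm loses participants selectively, and control-only selection gives 0.038. The documents do not describe what the control group receives, so there is no basis for saying that only one arm has something to abandon.
- A reader might infer that phone and calendar data could recover those lost. They contain neither gait speed nor the performance-based mediators. The recovery to 0.050 comes from an interim gait-speed visit. It is also unclear whether 4-weekly contact continues after someone stops attending, and only Phone-Fitt and the LLFDI are described as obtainable by phone; exercise engagement is by self-report under a section not available here.
- A reader might infer that the SAP restricts mediation to complete cases. It says nothing either way; that is the default when no rule is given. Exercise self-efficacy is a questionnaire with no stated mode, so a missed visit need not remove it.
- A reader might infer that anyone who stops attending disappears altogether. A participant seen at an earlier follow-up still enters that visit's change score.

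**Conclusion.** The point holds as a gap in specification with a cheap remedy. The stated treatment-control comparison uses only participants with both visits, its time point is unclear, and nothing assigns the better-suited model to that contrast or says how missing values enter the mediation models.

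Under the assumptions shown, a true 0.05 m/s could appear as anything from about 0.038 to about 0.070, depending on which arm has selective dropout and how strongly. With milder treated-arm selection it is 0.052-0.059, and under random or balanced dropout there is no bias. These figures show possible size; they do not predict direction.

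The mixed model's advantage requires that dropout depend on values already observed. It cannot repair dropout driven by unseen gait speed, and participants with only a baseline visit add little to it. Hence the need for a sensitivity analysis.

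**What to change.** 1. In the SAP's third and fourth paragraphs, make the arm comparison for gait speed the arm-by-visit contrast from the mixed model already named, at a stated visit. Include all enrolled participants in the group to which they were assigned and every observed visit. Keep the two-sample and paired t-tests as descriptive.
2. For the mediation models, multiply impute missing attribute and gait-speed values separately by arm from baseline and interim visits. Use LLFDI, Phone-Fitt, exercise engagement, and calendar falls and illnesses as auxiliary variables in the imputation model. State that these recover the missing information only in part.
3. Report one sensitivity analysis that shifts the imputed gait-speed values. Because the direction of bias is not known, allow the shift to differ by arm.

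The cost is SAP wording, some extra programming and a slightly more complex analysis. No new measurement is needed. If dropout proves to be random or balanced, the mixed model estimates the same difference as the t-test, so nothing is lost in bias.
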